9.0 RECORDS TO BE KEPT

- Subject Intake
- Subject Demographics
- Subject Consent Forms
- HIPAA Authorization Form
- Baseline and follow up survey data
- Coded C-CHESS use data
- Coded patient lab scores and health care utilization
- Coded transcripts from focus groups and interviews with patients
- Coded transcripts from interviews with clinic staff

Appendix A

CENTER FOR HEALTH ENHANCEMENT SYSTEMS STUDIES

Data Monitoring Committee (DMC)

For this project, the UW ICTR Data Monitoring Committee (DMC) will act as the Monitoring Board to oversee the study. The UW ICTR DMC is comprised of experienced members (core plus ad hoc) with expertise required to oversee this study. The DMC members will review protocol-specific reports created by statisticians using data pulled from the Research Electronic Data Capture (REDCap) data management tool. These standard reports will include an overview of study objectives, a review of actual and projected accrual rates, an evaluation of patient demographics for balance of randomization, and a summary of the number and seriousness of adverse events. An interim analysis of study results may be performed and source documents may be reviewed to allow the DMC to independently judge whether the overall integrity and conduct of the protocol remain acceptable based on data provided and reported by the Principal Investigator. This is a low risk study, but if we do conduct interim analyses our statistician will take into consideration the reduction in statistical power that will occur with each iteration. The DMC will make recommendations to the Principal Investigator that could include actions of continuation, modification, suspension, or termination.

The composition of the DMC contains experts qualified to review this protocol, including MDs in Pharmacy, Cardiology, Critical Care, and Psychiatry.

In providing oversight for the conduct of this study, the ICTR DMC will meet in-person annually during the 5-year study to review all adverse events. Additional meetings may be scheduled as determined by the DMC or as requested by the PI.

The predefined stopping points for this study will include excess rates of hospital re-admissions or quality of life determinates, exceeding 30% of pre-test values in both cases. We will submit all events, including both serious and non-serious adverse events and unanticipated problems, to the NHLBI, the DMC and the UW Health Sciences IRB in accordance with the following timeline:

What Event is Reported	When is Event Reported	By Whom is Event Reported	To Whom is Event Reported
Fatal or life-threatening unexpected, suspected serious adverse reactions	Within 7 calendar days of initial receipt of information	Investigator	Internal IRBs NHLBI and/or DMC
		Sponsor or designee ¹	FDA (if IND study)
Non-fatal, non-life-threatening unexpected, suspected serious adverse reactions	Within 15 calendar days of initial receipt of information	Investigator	Internal IRBs/ Institutional Officials NHLBI and/or DMC
		Sponsor or designee	FDA All participating investigators
Unanticipated adverse device effects	Within 10 working days of investigator first learning of effect	Investigator	Internal IRBs NHLBI and/or DMC
		Sponsor or designee	FDA (if IDE study)
Unanticipated Problem that is not an SAE	Within 14 days of the investigator becoming aware of the problem	Investigator	Internal IRBs/Institutional Officials, NHLBI and/or DMC
All Unanticipated Problems ²	Within 30 days of the IRB's	IRB	OHRP

	receipt of the report of the UP from the investigator.	Investigator ³	Internal IRBs and DMC
--	---	---------------------------	--------------------------

REDCap, a secure on-line data entry portal, will be used to standardize data capture between the multiple project sites. Project personnel at each study site will have the ability to enter data into REDCap via an individual user log-in. The user log-in can be configured to limit access to identifiable data, downloadable data sets, and data from other sites.

This Charter is for the Data Monitoring Committee (DMC) for the Center for Health Enhancement Systems Studies. The Charter will define the primary responsibilities of the DMC, its relationship with other trial components, its membership, and the purpose and timing of its meetings. The Charter will also provide the procedures for ensuring confidentiality and proper communication, the statistical monitoring guidelines to be implemented by the DMC, and an outline of the content of the reports that will be provided to the DMC.

UW Institute for Clinical and Translational Research Data Monitoring Committee Charter (Update 8/11/2016)

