1.0 STUDY OBJECTIVES

This project will test the use of an eHealth intervention called C-CHESS, to modify health behaviors and improve health outcomes in older adults with comorbid chronic diseases and health conditions.

Aim 1 Refine C-CHESS, using feedback from patients and primary care clinicians.

Aim 2 Conduct a randomized clinical trial to test 4 hypotheses:

1. *Primary outcomes:* Patients assigned to TAU+C-CHESS will have better quality of life and less primary care use (fewer visits) than those assigned to TAU+Internet.
2. *Secondary outcomes:* Patients assigned to TAU+C-CHESS will have improved composite scores; improved individual condition outcomes (mm Hg for hypertension, mg/dL for hyperlipidemia (LDL), HbA1c for diabetes, and pain for arthritis); and fewer symptoms from a list than patients assigned to TAU+Internet.
3. *Mediators:* Patients assigned to TAU+C-CHESS will have, compared with patients assigned to TAU+Internet, greater adherence to medications and appointments as well as improved competence,

relatedness, and autonomy.

4. *Moderators:* Improvements in primary outcomes for TAU+C-CHESS vs. TAU+Internet will be greater for women than men, those ≥ 75 vs. 65 to 74, and those with 3-5 chronic conditions vs. 6+.

Aim 3 Analyze data from the RCT and publish results.

Exploratory questions:

- Does C-CHESS reach a large proportion of targeted patients, get a large proportion of targeted clinicians to use C-CHESS, get a large proportion of patients to regularly use C-CHESS, and maintain that performance over time)?
- Does the use of specific C-CHESS services affect outcomes?
- Does the use of C-CHESS affect other health service use?

Primary Aim

Patients assigned to TAU+C-CHESS will have better quality of life and fewer primary care visits than those assigned to TAU+Internet.

C-CHESS will contain the Clinician Report to make it easier for PCPs to respond to important patient changes, pilot data suggested that primary care visits could be reduced. Reducing the number of primary care visits will both lessen provider burden and ultimately reduce healthcare costs.

Secondary Aim

Patients assigned to TAU+C-CHESS will have improved composite scores; improved individual condition outcomes (mm Hg for hypertension, mg/dL for hyperlipidemia (LDL), HbA1c for diabetes, and pain for arthritis); and fewer symptoms from a list than patients assigned to TAU+Internet.

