2.0 SELECTION OF SUBJECTS

Patient Recruitment: We will recruit 330 patients age ≥ 65 .

Patients are eligible for the study if they:

- 1) are ≥ 65 years old
- 2) have been treated in the clinic for at least the previous 18 months with no plans to leave during the study period

- 3) have ≥ 3 of the following chronic conditions:
 - Hypertension
 - Hyperlipidemia
 - Diabetes
 - Arthritis
 - BMI ≥ 30
 - Chronic Kidney disease
 - Chronic pain
 - COPD
 - Congestive heart failure
 - Arrhythmia/atrial fibrillation
- 4) report no current psychotic disorder that would prevent participation
- 5) have no acute medical problem requiring immediate hospitalization
- 6) do not have a visual or motor impairment that prevents them from using a computer
- 7) be able to read and sign the consent form in English
- 8) have no known terminal illness;
- 9) be willing to share health-related study data and
 - Systolic and diastolic BP
 - Weight
 - BMI
 - HDL/LDL
 - HbA1C
 - pain score
 - health care utilization: hospitalizations (admission and discharge), number of ER visits, urgent care visits, PC visits, specialty care visits, long-term care visits, and rehab visits
- 10) allow researchers to share information with their primary care physician

We will document and describe eligible people who choose not to participate.

Clinician Recruitment: 15 providers (salaried, credentialed staff) from 5 different clinic sites will be identified and recruited to complete 3 qualitative interviews each over the course of the study. Site staff will be identified by the clinic and contacted by the UW study coordinator. Details of the study and their participation will be explained and if they agree informed consent will be collected. Staff are eligible for the study if they:

- Allow monitoring of their C-CHESS usage
- Are willing to participate in 3 interviews to share information about technology use at their clinic and feedback related to C-CHESS.
- Have a patient participating in the intervention arm of this study

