8.0 STATISTICAL CONSIDERATIONS

Power analyses for primary and secondary outcomes. Our power analysis was based on Elder Tree pilot data and other studies that examined the impact of behavioral interventions on single chronic conditions.⁹⁵ A meta-analysis⁹⁶ of self-management interventions found significant effects on HbA1c for diabetics ($d = .36$), and on systolic blood pressure among hypertensives ($d = -.39$). Other studies found a moderate effect size ($d = .61$) on pain behavior⁹⁷ and a small effect on number of primary care visits ($d = .28$) when patients attended self-management and peer-support meetings.^{98,99}

Because effect sizes vary for interventions of chronic conditions, we want our expected effect sizes to be conservative and yet clinically meaningful. We therefore chose an effect size of $d = .40$ for our primary

outcomes (quality of life and primary care use) as well as individual condition measures (secondary outcomes) and the composite score based on them. Adequate power ($1-\beta = .80$, two-tailed $\alpha = .05$) would require a final sample of $N=200$ patients (100 per arm).¹⁰⁰ Since we will examine 4 clusters, with 3 conditions per cluster, we will need 132 per arm. Assuming 20% attrition, we will recruit $N=330$ patients (33 per arm per clinic). This should also be sufficient for detecting similar effect sizes (at a power of $1-\beta = .80$) for condition-specific changes in diabetes,¹⁰¹ hypertension,¹⁰² and arthritis.¹⁰³ The literature is less clear in hyperlipidemia but 50% of patients are non-adherent to statins,¹⁰⁴ and statins have a high effect size,¹⁰⁵ so our goal may be achievable.

Power for mediation and moderation analyses. Power for detecting parameter changes in the structural model was estimated using a procedure of Satorra and Saris¹⁰⁶ that approximates the non-central chi-square distribution. A total N of 220 patients will provide adequate power ($> .80$) to detect a group difference in a parameter by moderate .4 standard deviations. With an N of 264 in our primary analysis, we are confident our secondary analysis will have adequate power.

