7.3 Meeting Format

7.3.1. Open/Closed Meetings

The ICTR DMC does not meet the definition of a “governmental body” as defined in sec. 19.82(1), Wis. Stats., in that it was not created by constitution, statute, ordinance, rule or order. As a result, the ICTR DMC does not operate consistent with the Wisconsin Open Meetings law. The use of the term “open session” herein describes that portion of a meeting in which the PI and/or his/her staff are invited to be present at the meeting.

The use of the term “closed session” herein describes that portion of the meeting when only the ICTR DMC members, staff from the SDAC, and invited guests (such as those with a particular needed expertise) are present at the meeting. Such terms should be not be given their meaning under the Wisconsin Open Meetings law.

7.3.2 Format of Meetings when serving as the DMC for the UW-Madison clinical research infrastructure.

When acting as an institution-wide DMC to monitor subject safety across the clinical research infrastructure, the ICTR DMC meetings will consist of only closed sessions. Attendance to these meetings will be restricted to ICTR DMC members and administrative staff, staff from the SDAC, and any invited guests. NHLBI staff representatives will be voted in and will be allowed to attend as invited guests.

7.3.3 Format of Meetings when serving as the DMC for investigator-initiated clinical research protocols.

ICTR DMC meetings will follow Robert's Rules of Order in all cases in which they are applicable and not inconsistent with ICTR DMC standard operating procedures. The meetings will consist of open and closed portions. During the initial open portion of a meeting, the PI and his/her designated staff may be invited to make brief presentations and be available for questions from and discussions with the DMC members without revealing interim data. The open session will only discuss aggregate data to reduce the risk of misleading conclusions. The closed session will be restricted to ICTR DMC members and administrative staff, staff from the SDAC, and any invited guests.⁴ The closed session will discuss accumulating data by assigned and unblended treatment group.

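### The predefined stopping points compare with pre-test values instead of the concurrent control arm and give no harmful direction for quality of life, so they can signal without a treatment effect or miss harm

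*Combined protocol and SAP*

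**What the plan says.** Appendix A contains the only protocol-specific stopping criterion: "The predefined stopping points for this study will include excess rates of hospital re-admissions or quality of life determinates, exceeding 30% of pre-test values". The sentence applies the same reference to re-admissions and to quality of life ("exceeding 30% of pre-test values in both cases"). It does not define the pre-test window, the quality-of-life quantity, the unit (patient, arm or pooled sample), a minimum number of patients or events, or any statistical boundary.

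The protocol's Sections 6.0 and 8.0, which hold the statistical plan, contain no stopping rule, although Section 6.0 of the DMC charter expects stopping rules to be specified there. Charter Section 7.2.2 has the committee meet before the study starts to help set its criteria for discontinuation in advance. Charter Section 7.3.3 gives it by-arm data: "The closed session will discuss accumulating data by assigned and unblended treatment group". Better quality of life is a primary hypothesis in Section 1.0: "Patients assigned to TAU+C-CHESS will have better quality of life".

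**The concern.** A before-after trigger discards what randomisation provides. Participants are 65 or older with at least three chronic conditions and are followed for 18 months. If re-admissions rise in both arms, for instance through ageing, the rule registers the rise as a signal although C-CHESS contributes nothing. If instead the control arm improves while the C-CHESS arm does not, patients on C-CHESS are worse off than they would have been, yet nothing has moved relative to pre-test.

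For re-admissions, the word excess supplies a direction. For quality of life nothing does. On a scale where higher is better, exceeding the pre-test value is the hypothesised benefit, so read literally an improvement counts toward the trigger and a deterioration does not.

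At stake is whether the trial's one predefined trigger tells the committee anything about harm from C-CHESS.

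**Working it through.** **Plan's own figures.** The stopping rule has no stated error rate to reproduce. The sample size can be checked, because it fixes the number per arm. With d = 0.40, two-sided alpha 0.05 and power 0.80, 2(1.960 + 0.842)²/0.40² = 98.1, or 99 per arm with the t correction; Section 8.0 states 100. Its later figure of 132 per arm gives 264, and 264/(1 − 0.20) = 330, so 165 per arm at 1:1.

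**Re-admissions.** Assumptions, since the documents give no rate:
- r = 0.03, 0.05, 0.10 or 0.20 re-admissions per patient per window
- equal pre-test and post-test windows
- Poisson counts, 165 patients per arm, one look
- the limit is read as a 30% rise, applied to the C-CHESS arm

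With m = 165r expected events, X the reference count and Y the C-CHESS post-test count, P(trigger) = P(Y > 1.3X) = Σₓ P(X = x)·P(Y > 1.3x).

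The means of (X, Y) in each scenario are:
- A, no change anywhere: (m, m) under either comparator
- B, 20% rise in both arms: (m, 1.2m) versus pre-test; (1.2m, 1.2m) versus control
- C, 50% rise in both arms: (m, 1.5m) versus pre-test; (1.5m, 1.5m) versus control
- D, control falls 30%, C-CHESS flat: (m, m) versus pre-test; (0.7m, m) versus control

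| r | m | A, either | B, pre-test | B, control | C, pre-test | C, control | D, pre-test | D, control |
|---|---|---|---|---|---|---|---|---|
| 0.03 | 4.95 | 0.350 | 0.455 | 0.332 | 0.602 | 0.309 | 0.350 | 0.568 |
| 0.05 | 8.25 | 0.298 | 0.430 | 0.278 | 0.622 | 0.257 | 0.298 | 0.571 |
| 0.10 | 16.5 | 0.229 | 0.407 | 0.206 | 0.674 | 0.180 | 0.229 | 0.598 |
| 0.20 | 33.0 | 0.145 | 0.367 | 0.123 | 0.739 | 0.097 | 0.145 | 0.637 |

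Scenarios A, B and C have no treatment effect, so every trigger in them is false. Under C the pre-test rule gets worse as events accumulate, while the control comparison gets better. In D, C-CHESS is 1/0.7 = 1.43 times control, and the pre-test rule triggers no more often than under A.

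Column A isolates a second defect. The chance rate is the same under either comparator, because it comes from having no boundary or minimum event count. Overdispersion raises it slightly (0.36 to 0.20 with negative-binomial dispersion 3), and repeated looks can only raise it further. By contrast, an exact conditional between-arm test at one-sided 0.025, single look, triggers in 0.012 to 0.020 of cases with no difference between arms.

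**Quality of life.** The mean and SD are not given. If the control arm does not change, an effect d equals d × (SD/mean) as a fraction of the mean. For d = 0.40:
- SD/mean 0.15: 0.40 × 0.15 = 6%
- SD/mean 0.30: 0.40 × 0.30 = 12%
- 30% is reached only at SD/mean = 0.30/0.40 = 0.75

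Conversely, a 30% rise in the group mean needs d = 0.30/0.15 = 2.0 at SD/mean 0.15 and d = 0.30/0.30 = 1.0 at SD/mean 0.30. A 30% shift in a group mean of 165 by chance is negligible, about 1 in 10,000 at most even at SD/mean 1.0.

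If the rule is read per patient, the SD of change is SD·√(2(1 − ρ)). With ρ from 0.5 to 0.7 and SD/mean from 0.15 to 0.30, between 1% (z = 0.30/0.116 = 2.58) and 32% (z = 0.30/0.30 = 1) of patients move beyond 30% in one direction or the other without any true change.

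**The case against.** The strongest reply is that the sentence does not act alone. The committee helps set discontinuation criteria before the study starts (charter Section 7.2.2). Protocol-specific detail may sit in an addendum (charter Section 1.1), and none is included in the documents. The committee sees by-arm data and only recommends (charter Section 7.4). The list of stopping points is introduced as inclusive, so it may not be exhaustive. The study describes itself as low risk. All of this stands and limits the consequence, but none of it changes the stated comparator or supplies a direction.

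A reader might also infer four stronger points that the documents do not support:

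- **That the pre-test comparator causes the chance triggers.** It does not; column A is the same for both comparators.
- **That re-admissions must rise in both arms because entry selects a low pre-test level.** Section 2.0 requires that patients "have no acute medical problem requiring immediate hospitalization", which concerns status at entry, not past re-admissions. Recruitment at scheduled clinic appointments (Section 3.0) could favour recent users and push the other way. With the window undefined, a shared rise is possible, not shown.
- **That the planned benefit would trip the rule.** At group-mean level a 30% rise needs an effect well above d = 0.40 on usual scales.
- **That the rule is met with no change at all, because any unchanged value exceeds 30% of itself.** The wording allows this, but its reference to excess rates and its place in a safety-oversight appendix make a 30% rise the sensible reading.

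**Conclusion.** The concern holds for the comparator and the missing direction. As written, the rule cannot separate harm from C-CHESS from a change common to both arms. Under the stated assumptions, a shared 50% rise with no treatment effect triggers it with probability 0.60 to 0.74, against 0.31 to 0.10 versus control; for a shared 20% rise the figures are 0.455 to 0.37 against 0.33 to 0.12. When control falls 30% and C-CHESS stays flat, it triggers with probability only 0.35 to 0.145, against 0.57 to 0.64 versus control.

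The missing boundary is a separate defect, which a change of comparator would leave in place. The missing quality-of-life direction is mainly a gap in wording at group-mean level and matters more if the rule is applied patient by patient.

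The probabilities depend on assumed event rates, equal windows and Poisson counts; the ordering under a shared rise does not depend on the particular rate within the range tried. The practical consequence is modest, and the primary estimate is unaffected. The sentence should still be changed, because it is the only predefined trigger and the data for a valid comparison already reach the committee.

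**What to change.** Reword the Appendix A sentence, in agreement with the DMC, so that:

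- both triggers compare C-CHESS with the concurrent control arm in the closed report;
- the harmful direction is written for each measure, and the quality-of-life quantity, the unit of assessment and the time window are named;
- a trigger counts as met only when the confidence interval for the between-arm difference supports harm, not when an interval is merely displayed beside a crossed percentage.

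The size of the limit stays with the DMC and sponsor. The rule should then be placed in, or cross-referenced from, the statistical plan, so that it agrees with charter Sections 6.0 and 7.2.2.

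The cost is a short rewording and the committee's agreement; by-arm data are already provided for. The price is that a tested boundary reacts more slowly when events are few, so in that period the committee relies on its judgement of the by-arm listings.

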1.1 INTRODUCTION

The UW Institute for Clinical and Translational Research (UW ICTR) has developed an organizational structure to provide the appropriate oversight and monitoring of clinical research to ensure the safety of participants and the validity and integrity of the data.¹

To meet these needs, UW ICTR will convene a group of multidisciplinary experts to:

1. monitor subject safety and data integrity across the UW-Madison clinical research infrastructure, and
2. serve as the Data Monitoring Committee (DMC) for investigator-initiated clinical research protocols that require and request an independent DMC

The UW ICTR Data Monitoring Committee (ICTR DMC) covers responsibilities of entities often referred to as a Data and Safety Monitoring Committee (DSMC) or a Data and Safety Monitoring Board (DSMB).

The term “clinical research” is used throughout this document as defined by the National Institutes of Health (NIH). The NIH definition of clinical research is “(1) Patient Oriented Research: Research conducted with human subjects (or on material of human origin such as tissues, specimens and cognitive phenomena) for which an investigator (or colleague) directly interacts with human subjects. Patient-oriented research includes: (a) mechanisms of human disease, (b) therapeutic interventions, (c) clinical trials, and (d) development of new technologies. (2) Epidemiologic and behavioral studies; (3) Outcomes research and health services research.²

Changes to this Charter may not be made without approval by the ICTR DMC. Protocol specific information should be included in an addendum or memorandum of understanding approved by the DMC.

